10.6. Pregnancy

Pregnancy of a female subject during the clinical study is not considered an adverse event, and an elective abortion without complications (not applicable for therapeutic abortion) or hospitalization for live birth of a healthy newborn is also not considered an adverse event.

However, if a female subject becomes pregnant during the clinical study, the subject shall be dropped out from the clinical study, and the investigator shall complete a pregnancy report form and submit it to the clinical study sponsor within 24 hours of becoming aware of the pregnancy. In addition, even for cases in which a pregnancy is confirmed within 90 days after the end of the clinical study (discontinuation), the investigator shall complete a pregnancy report form and submit it to the clinical study sponsor within 24 hours of becoming aware of the pregnancy. The investigator shall submit follow-up reports on the subsequent progress of the pregnant woman and the fetus until birth even if the subject discontinues participation in the clinical study or completes the clinical study.

Serious maternal complications, spontaneous abortions, ectopic pregnancy, stillbirths, neonatal deaths, congenital malformations, etc., are considered serious adverse events, and the investigator shall report them according to the procedures in section 10.5.3 Reporting of Serious Adverse Events.

10.7. Overdosing

Overdosing is defined as an accidental or intentional administration of a drug at a dose considered by the

investigator to be excessive and medically significant. The investigator will consider overdosing as a significant medical event and report it to the sponsor, regardless of the adverse event outcome.

11. Data Analysis and Statistical Considerations

11.1. Analysis Set

The main analysis of efficacy evaluation of this clinical study will be performed on the full analysis set (FAS), and the analysis on the per-protocol set (PPS) will be performed as a supplement. The safety evaluation analysis will be performed as actually administered in the safety set. The exploratory evaluation analysis will be performed on the FAS and PPS, and the demographic and the characteristics prior to administration will be analyzed in all randomized subjects.

11.1.1. Efficacy Evaluation Set

Full Analysis Set (FAS)

This includes subjects who received at least 1 dose of the investigational product after randomization and had at least 1 evaluation with the PSP-rating scale after the administration of the investigational product and up to the end of the clinical study.

Per-Protocol Set (PPS)

Among the subjects included in FAS, the subjects who completed the clinical study without major protocol violations are included. Subjects with major protocol violations (see 5.5.3 Protocol Violations) may be excluded from PPS.

Exclusion from PPS will be decided through a blind meeting prior to database lock, after comprehensively discussing whether the clinical study was affected.

11.1.2. Safety Evaluation Set

Safety set

Among the subjects who were administered at least one dose of the investigational product after randomization, subjects whose safety-related data were evaluated at least once after the administration will be included.

11.2. Statistical Analysis Method

11.2.1. General Principles of Analysis

All statistical analyses will use SAS® (version 9.4 or higher; SAS Institute, Cary, NC, USA). In principle, all tests are two-sided tests under a significance level of 5% unless otherwise specified. The efficacy evaluation of this clinical study will perform analysis according to the “intention-to-treat principle,” and the safety evaluation will perform analysis as actually administered. Continuous data will present the number of subjects observed, mean, standard deviation, median, minimum, and maximum, while categorical data will present frequencies and percentages by category.

11.2.2. Method of Handling Missing Data

When analyzing the efficacy endpoints and exploratory endpoints, in the case of utilizing the mixed-effect model repeated measure (MMRM) method, the available data will be analyzed as they are since the method does not require the replacement of missing values. If missing values occur in the safety endpoints and exploratory endpoints analyzed by methods other than MMRM, analysis will be performed only on the collected data without imputation.

11.2.3. Covariate Adjustment

Efficacy endpoints will be analyzed with adjustments for the baseline values as well as for the age and sex.

11.2.4. Interim Analysis

No interim analysis will be performed before the end of the clinical study. However, an interim analysis related to the safety of this clinical study may be conducted when a serious issue related to safety is discovered and the need is recognized through a meeting or a deliberation of the investigator or principal investigator.

11.2.4.1. Independent Data Monitoring Committee (IDMC)

A discussion may be held according to the charter of an independent data monitoring committee (IDMC) composed of clinical experts not including the principal investigator, sub-investigators, and sponsor to make objective decisions on details related to safety by clarifying the judgment on safety findings obtained during the course of this clinical study.

11.2.4.2. Safety Monitoring

The principal investigator will act as the protocol safety manager based on the risk level of this clinical study, and the principal investigator at each study site will monitor the safety of the subjects participating in the relevant study site in accordance with the protocol during the clinical study.

Whenever serious adverse events and adverse drug reactions occur, the principal investigator will collect and review the relevant subject's data and safety information. If adverse events, unexpected problems, and protocol noncompliance cases should occur, the principal investigator shall submit reports to the sponsor (including the CRO) and the IRB in accordance with the protocol, IRB regulations of each study site, KGCP, and relevant regulations, and also submit reports to the Ministry of Food and Drug Safety if necessary. In addition, in accordance with the criteria for early termination or discontinuation of the clinical study in section 7.2, reports will be submitted to the sponsor in a timely manner if any efficacy and safety information that can significantly impact the continuation of the clinical study should emerge, and the sponsor will discuss and decide on the continuation of the clinical study according to the sponsor's standard operating procedure (SOP).

11.2.5. Multiple Comparisons and Multiplicity

Given that this is a Phase 2 clinical study for therapeutic exploratory purposes, no correction of type I error due to comparisons with the control group were considered for each of the study groups (GV1001 0.56 mg/day, 1.12 mg/day).

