3.3 Determination of the Sample Size

Total number of subjects: 75 subjects (75 subjects in total with 25 subjects per group considering a dropout rate of 20%)

	Study Group 1	Study Group 2	Control Group	Total Number of Subjects
Number of Subjects	20	20	20	60
Number of Subjects Considering Dropout (20%)	25	25	25	75

This is a Phase 2a exploratory clinical study conducted for the purposes of collecting initial safety and efficacy information on the investigational product GV1001 in patients with progressive supranuclear palsy as well as providing the basis for design, evaluation items, and evaluation methods for subsequent clinical studies. Since this is a study to estimate the clinically significant effect size to demonstrate the efficacy of this investigational product, the number of subjects was not calculated based on statistical considerations. The minimum number of subjects required in a pilot study is 12 subjects²⁾ and approximately 30 subjects can be considered according to the rule of thumb^{3), 4)}. Therefore, by combining these, it is intended to set 20 subjects per group, and a total of 75 subjects with 25 subjects per group will be enrolled considering a dropout rate of 20%.

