5. GENERAL CONSIDERATIONS FOR SUMMARIES AND ANALYSES

5.1 Significance Level

Unless otherwise specified, all statistical tests will be two-sided hypothesis tests performed at the 5% level of significance and all confidence intervals will be two-sided 95% confidence intervals.

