9.1.2 Method of Analysis

Descriptive statistics (number of subjects observed, mean, standard deviation, median, minimum, and maximum) will be presented by treatment group for each visit and the change from the baseline in the total score of the PSP-rating scale after 24 weeks (6 months) of investigational product administration. To test the difference between each study group and the control group (GV1001 0.56 mg/day vs. control group, GV1001 1.12 mg/day vs. control group), an MMRM analysis will be conducted with the treatment groups, visits, and interactions between the visits and the treatment groups set as fixed effects, and the subjects set as the random effect, as well as considering the baseline values, age, and sex as covariates. The results of the MMRM analysis will be summarized by LSM and standard error (SE) for each treatment group, the LSM difference between the study groups and the control group (GV1001 0.56 mg/day vs. control group, GV1001 1.12 mg/day vs. control group) and its 95% confidence interval as well as the two-side p-value.

Additionally, testing the difference within each treatment group will be conducted by the same MMRM analysis.

MMRM constructed as follows

- Dependent Variable: Change from baseline in total score of PSP-rating
- Fixed Effects
 - Fixed Continuous Effects: Baseline PSP-rating, Age
 - Fixed Categorical Effects: Treatment, Visit, Visit*Treatment, Sex
- Repeated Effect: Visit
- Random Effect: Subject
- Covariance Structure: Unstructured (UN)

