9.1.3 Interpret the Result

The Superiority of each study group to placebo is confirmed when the p-value for the interaction effect at 24 weeks is below 0.05.

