3.4. Rationale for Dose Setting

The dose of the investigational product to be used in this clinical study was determined by the process of deriving the maximum recommended starting dose for human clinical studies on new drugs.

[Redacted content block]

Summarizing the above results, the safe starting dose for the PSP clinical study was 0.56 mg/day ([REDACTED]), and the second dose was determined as 1.12 mg/day ([REDACTED]).

In addition, at the previously implemented doses of GV1001 0.56 to 1.12 mg/day used in patients approved for therapeutic use of the drug, no significant adverse events were reported, similar to other clinical studies, and significant clinical improvements were shown in the change of the PSP-RS score. Moreover, since results of improvement could be observed in other clinical symptoms, it was determined that the dose of 0.56 to 1.12 mg/day is appropriate in this clinical study.

Based on the above considerations, this clinical study intends to conduct a final validation on the efficacy and safety of two doses of GV1001 0.56 mg/day and 1.12 mg/day.

4. Study Objectives

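### SAP 9.1.3 declares superiority of each dose confirmed at an unadjusted p<0.05, although the protocol waives correction only because the trial is exploratory; with two doses, the chance of at least one false declaration is about 9%

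*Combined protocol and SAP*

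**What the plan says.** **Protocol.** Section 11.2.5 opens with its reason, "Given that this is a Phase 2 clinical study for therapeutic exploratory purposes", and concludes that "no correction of type I error due to comparisons with the control group were considered for each of the study groups". Section 11.2.1 sets the general level: "In principle, all tests are two-sided tests under a significance level of 5% unless otherwise specified". Section 11.2.8.1 (primary analysis) asks for LSMs, LSM differences from control, 95% confidence intervals and p-values. It does not say what result would count as success.

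**SAP.** Section 5.1 repeats the level: "all statistical tests will be two-sided hypothesis tests performed at the 5% level of significance". Section 9.1.2 makes two primary comparisons against the same placebo arm: "GV1001 0.56 mg/day vs. control group, GV1001 1.12 mg/day vs. control group". Section 9.1.3 then adds a decision rule that the protocol lacks: "The Superiority of each study group to placebo is confirmed" when the 24-week p-value is below 0.05. It states no adjustment and no direction. The body of the SAP has no section on multiplicity. Section 3.5, the table of changes from the protocol, lists five added secondary endpoints and the subgroup analysis, but not this rule.

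**Sample size.** SAP 3.3 says that "the number of subjects was not calculated based on statistical considerations", and protocol 11.4 says the same. The stated aim is to estimate an effect size.

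**The concern.** The waiver and the decision rule rest on different ideas of what the trial is for. Leaving two comparisons uncorrected is a fair choice when the output is estimates and nominal p-values to guide a later trial. It does not fit a rule that turns one nominal p-value into confirmed superiority. The SAP keeps the waiver, drops the condition attached to it, and does not record that it has done so.

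What is at stake is the headline conclusion. A trial with about 20 evaluable subjects per arm, not sized for any test, could be reported as having confirmed the superiority of a dose. It has two chances to reach that statement and no control over the pair. The estimates and intervals would not be affected.

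**Working it through.** **Inputs**
- Level: 0.05 per test, two-sided (SAP 5.1, protocol 11.2.1).
- Comparisons under the rule: 2, sharing one placebo arm (SAP 9.1.2 and 9.1.3).
- Allocation: 1:1:1 (SAP 3.2, protocol 6.3).
- Arm size: 20, raised to 25 for 20% dropout (SAP 3.3).
- Effect size and SD: not given, and not needed for an error rate under no effect.

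**Step 1. The plan's own figures.** 20 / (1 − 0.20) = 25 per arm and 3 × 25 = 75 in total, as stated. The only error rate the documents state is 5% per test. They give no rate for the pair of comparisons.

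**Step 2. Correlation of the two contrasts.** With n per arm and common variance σ², each difference from placebo has variance 2σ²/n. The two differences share the placebo mean, so their covariance is σ²/n. The correlation is (σ²/n) / (2σ²/n) = 0.5.

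**Step 3. At least one declaration when neither dose works, either direction.** This is the rule as written, since it names no direction.
- P(dose 1 significant) = P(dose 2 significant) = 0.05.
- P(both significant), bivariate normal with correlation 0.5 and cut-off 1.96: 0.00925.
- P(at least one) = 0.05 + 0.05 − 0.00925 = 0.0907, or about 9.1%.

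**Step 4. The same, counting only benefit.**
- One comparison: 0.025.
- At least one of two: 0.0454, or about 4.5%.
- Ratio: 0.0454 / 0.025 = 1.8. Step 3 gives the same ratio: 0.0907 / 0.05 = 1.8.

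**Step 5. Sensitivity.** Replacing the normal with a t distribution on 54 to 72 degrees of freedom (assumed from 20 to 25 subjects per arm) gives 9.02% to 9.04%, and 4.5% in one direction. If the two tests were independent, the figure would be 1 − 0.95² = 9.75%. The Bonferroni bound is 10%.

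**Step 6. The passages side by side.**

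| Place | What it supports |
|---|---|
| Protocol 11.2.5 | No correction, because exploratory |
| Protocol 11.2.8.1 | Estimates, intervals and p-values; no success rule |
| SAP 3.3, protocol 11.4 | Effect-size estimation; not statistically sized |
| SAP 9.1.3 | Superiority confirmed for each dose at an unadjusted p<0.05 |
| SAP 3.5 | No entry for the rule in 9.1.3 |

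The first three rows agree with one another. The fourth does not fit them, and the fifth shows that the departure was not declared.

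**The case against.** The strongest reply is that an exploratory phase 2a trial needs no multiplicity correction, that the plan says so openly, and that no promised error rate is broken. Most of this stands. The waiver is legitimate. The SAP calls the study exploratory in 3.2 and 3.3, and a careful reader would treat the p-values as nominal. But this reply defends the missing correction. It does not defend the confirmatory wording, which is the fault.

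Four stronger readings are tempting, and the documents do not support them.

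- **That each dose's claim has a 9% false-positive rate.** It does not. SAP 9.1.3 judges each dose separately, and each stays at 5%. The 9.1% is the chance of at least one false declaration out of two.
- **That a stated level is exceeded.** Only a per-test level is stated. No level is promised across the two doses, and protocol 11.2.5 disclaims one.
- **That the many secondary tests add to the problem.** The confirming rule sits under SAP 9.1 and covers only the primary endpoint. SAP 9.2 attaches no such rule, so uncorrected secondary tests fit the exploratory stance.
- **That protocol 3.4 shows a confirmatory trial.** It says that "this clinical study intends to conduct a final validation on the efficacy and safety of two doses". That sentence closes a partly redacted dose rationale and is not a decision rule. The protocol's primary objective is to explore efficacy.

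It is also fair to say that superiority usually means benefit, and on that reading the chance of at least one false declaration is 4.5%, below 5%. The matching single-comparison figure is then 2.5%, so the inflation by a factor of 1.8 is unchanged.

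**Conclusion.** The point holds as a conflict between the decision rule and the basis for waiving correction. SAP 9.1.3 as written would let the trial state a confirmed result that protocol 11.2.5, protocol 11.2.8.1 and the sample-size rationale do not support.

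The size is moderate. When neither dose works, the chance of at least one declaration is about 9.1% in either direction against 5% for one comparison, or about 4.5% against 2.5% if only benefit counts. These figures assume equal arms and a common variance, hence the correlation of 0.5. Unequal dropout would move them only slightly. They also take the p-value in 9.1.3 to be that of each dose's week-24 comparison with placebo.

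The fault lies in the strength of the conclusion, not in the uncorrected comparisons, which the plan declares. The sponsor should correct it, because it governs what the trial may claim.

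**What to change.** Before unblinding (the third step in SAP 4.2), replace SAP 9.1.3 with wording such as: *The week-24 LSM differences between each dose and placebo are reported with 95% confidence intervals. P-values are nominal and are not adjusted for the two doses. No claim of confirmed superiority is made.* This brings the SAP back to protocol 11.2.5 and 11.2.8.1. It needs no protocol amendment, no further data and no new analysis. The cost is that the sponsor gives up the word *confirmed*.

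Only if the sponsor wants to keep a formal claim should it pre-specify a procedure that holds two-sided 5% over the two doses, and list it in SAP 3.5 as a departure from protocol 11.2.5. There are two simple choices:
- **Holm:** test the smaller p-value at 0.025 and, if it passes, the larger at 0.05.
- **Fixed sequence:** test a first-named dose at 0.05 and the other only if the first passes.

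For scale, a Dunnett adjustment puts the per-comparison level at about 0.027. Plain Bonferroni at 0.025 each gives about 4.6% over the pair. The cost of this route is a stricter test for one comparison, or one that depends on the other, in a trial not sized for either.

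The sentence in protocol 3.4 need not change. It is background, and editing it would amend the protocol under protocol 13.5.1.

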11.2.6. Subgroup Analysis

Subgroup analysis will not be considered in this clinical study.

11.2.7. Demographic Information and Other Characteristics Prior to Treatment

The demographic information and other characteristics prior to treatment of the subjects included in this clinical study will be summarized by treatment group. Continuous variables will present the number of subjects observed, mean, standard deviation, median, minimum, and maximum. In addition, depending on whether the assumption of normality is satisfied, the two-sample t-test (if normality assumption is satisfied) or Wilcoxon's rank-sum test (if normality assumption is not satisfied) will be used to compare each study group with the control group (GV1001 0.56 mg/day vs. control group, GV1001 1.12 mg/day vs. control group). Categorical variables will present frequencies and percentages, and depending on whether cells with an expected frequency less than 5 exceed 20% of the total cells, Pearson's chi-square test (if the cells with an expected frequency less than 5 does not exceed 20% of the total cells) or Fisher's exact test (if the cells with an expected frequency less than 5 exceed 20% of the total cells) will be used to compare each study group with the control group (GV1001 0.56 mg/day vs. control group, GV1001 1.12 mg/day vs. control group).

Medical history will be standardized using the Medical Dictionary for Regulatory Activities (MedDRA), and the frequency, percentage, and number of cases will be presented by group for each standardized medical history. Prior/concomitant medications will be standardized by the ATC code of the WHO Drug Dictionary, and the

frequency and percentage of subjects as well as the number of cases will be presented by group for each standardized concomitant medication.

11.2.8. Efficacy Analysis

11.2.8.1. Primary Efficacy Analysis

Descriptive statistics (number of subjects observed, mean, standard deviation, median, minimum, and maximum) will be presented by treatment group for the change from the baseline in the total score of the PSP-rating scale after 24 weeks (6 months) of investigational product administration. To test the difference between each study group and the control group (GV1001 0.56 mg/day vs. control group, GV1001 1.12 mg/day vs. control group), an MMRM analysis will be conducted with the treatment groups, visits, and interactions between the visits and the treatment groups set as fixed effects, and the subjects set as the random effect, as well as considering the baseline values, age, and sex as covariates. The results of the MMRM analysis will be summarized by LSM and standard error (SE) for each treatment group, the LSM difference between the study groups and the control group (GV1001 0.56 mg/day vs. control group, GV1001 1.12 mg/day vs. control group) and its 95% confidence interval as well as the two-side *p*-value.

11.2.8.2. Secondary Efficacy Analysis

- 1) Change from the baseline in the total score of PSP-rating scale after 12 weeks (3 months) of investigational product administration

Descriptive statistics (number of subjects observed, mean, standard deviation, median, minimum, and maximum) will be presented by treatment group for the change from the baseline in the total score of the PSP-rating scale after 12 weeks (3 months) of investigational product administration. To test the difference between each study group and the control group (GV1001 0.56 mg/day vs. control group, GV1001 1.12 mg/day vs. control group), an MMRM analysis will be conducted with the treatment groups, visits, and interactions between the visits and the treatment groups set as fixed effects, and the subjects set as the random effect, as well as considering the baseline values, age, and sex as covariates. The results of the MMRM analysis will be summarized by LSM and standard error (SE) for each treatment group, the LSM difference between treatment groups and its 95% confidence interval, and the two-sided *p*-value.

- 2) Change from the baseline in the Montreal Cognitive Assessment - Korea (MoCA-K) after 12 weeks (3 months) and 24 weeks (6 months) of investigational product administration

Descriptive statistics (number of subjects observed, mean, standard deviation, median, minimum, and maximum) will be presented by treatment group for the change from the baseline in MoCA-K after 12 weeks (3 months) and 24 weeks (6 months) of investigational product administration. To test the difference between each study group and the control group (GV1001 0.56 mg/day vs. control group, GV1001 1.12 mg/day vs. control group), an MMRM analysis will be conducted with the treatment groups, visits, and interactions between the visits and the treatment groups set as fixed effects, and the subjects set as the random effect, as well as considering the baseline values, age, and sex as covariates. The results of the MMRM analysis will be summarized by LSM and standard error (SE) for each treatment group, the LSM difference between treatment groups and its 95% confidence interval, and the two-sided *p*-value.

- 3) Change from the baseline in the Korean Frontal Assessment Battery (K-FAB) after 12 weeks (3 months) and 24 weeks (6 months) of investigational product administration

Descriptive statistics (number of subjects observed, mean, standard deviation, median, minimum, and maximum) will be presented by treatment group for the change from the baseline in K-FAB after 12 weeks (3 months) and 24 weeks (6 months) of investigational product administration. To test the difference between each study group and the control group (GV1001 0.56 mg/day vs. control group, GV1001 1.12 mg/day vs. control group), an MMRM analysis will be conducted with the treatment groups, visits, and interactions between the visits and the treatment groups set as fixed effects, and the subjects set as the random effect, as well as considering the baseline values, age, and sex as covariates. The results of the MMRM analysis will

be summarized by LSM and standard error (SE) for each treatment group, the LSM difference between treatment groups and its 95% confidence interval, and the two-sided *p*-value.

- 4) Change from the baseline in the England & Schwab Activity of Daily Living (ES ADL) scale after 12 weeks (3 months) and 24 weeks (6 months) of investigational product administration
Descriptive statistics (number of subjects observed, mean, standard deviation, median, minimum, and maximum) will be presented by treatment group for the change from the baseline in ES ADL after 12 weeks (3 months) and 24 weeks (6 months) of investigational product administration. To test the difference between each study group and the control group (GV1001 0.56 mg/day vs. control group, GV1001 1.12 mg/day vs. control group), an MMRM analysis will be conducted with the treatment groups, visits, and interactions between the visits and the treatment groups set as fixed effects, and the subjects set as the random effect, as well as considering the baseline values, age, and sex as covariates. The results of the MMRM analysis will be summarized by LSM and standard error (SE) for each treatment group, the LSM difference between treatment groups and its 95% confidence interval, and the two-sided *p*-value.
- 5) Change from the baseline in the score of each domain of the PSP-rating scale after 12 weeks (3 months) and 24 weeks (6 months) of investigational product administration
Descriptive statistics (number of subjects observed, mean, standard deviation, median, minimum, and maximum) will be presented by treatment group for the change from the baseline in the score of each domain of the PSP-rating scale after 12 weeks (3 months) and 24 weeks (6 months) of investigational product administration. To test the difference between each study group and the control group (GV1001 0.56 mg/day vs. control group, GV1001 1.12 mg/day vs. control group), an MMRM analysis will be conducted with the treatment groups, visits, and interactions between the visits and the treatment groups set as fixed effects, and the subjects set as the random effect, as well as considering the baseline values, age, and sex as covariates. The results of the MMRM analysis will be summarized by LSM and standard error (SE) for each treatment group, the LSM difference between treatment groups and its 95% confidence interval, and the two-sided *p*-value.
- 6) Change from the baseline in the score of each item of the PSP-rating scale after 12 weeks (3 months) and 24 weeks (6 months) of investigational product administration
Descriptive statistics (number of subjects observed, mean, standard deviation, median, minimum, and maximum) will be presented by treatment group for the change from the baseline in the score of each item of the PSP-rating scale after 12 weeks (3 months) and 24 weeks (6 months) of investigational product administration. To test the difference between each study group and the control group (GV1001 0.56 mg/day vs. control group, GV1001 1.12 mg/day vs. control group), an MMRM analysis will be conducted with the treatment groups, visits, and interactions between the visits and the treatment groups set as fixed effects, and the subjects set as the random effect, as well as considering the baseline values, age, and sex as covariates. The results of the MMRM analysis will be summarized by LSM and standard error (SE) for each treatment group, the LSM difference between treatment groups and its 95% confidence interval, and the two-sided *p*-value.

